Specific aim #1: Define functional nausea (FN) as an entity subdivided by measures of arousal, anxiety and gastric motor function.

Hypothesis: Adolescents with chronic nausea form subgroups based on clinical, physiologic and psychological parameters: 1) FN: characterized by high anxiety and emotional arousal, autonomic imbalance/low vagal tone and absence of major foregut dysmotility, 2) gastroparesis, and 3) poor gastric compliance. We will separate FN from other groups by clinical questionnaires, autonomic tests (heart rate variability) and gastric motility tests (gastric emptying, accommodation tests).

Specific aim #2: Demonstrate that resting state functional brain connectivity is different in female adolescents with FN compared to gender and age-matched healthy controls.

Hypothesis: Adolescents with FN will have altered rsFC between brain regions associated with emotional arousal neurocircuits (amygdala) and the top-down regulation of these by the prefrontal cortex. There will be decreased resting state functional connectivity between the ventromedial prefrontal cortex (vmPFC) and amygdala in adolescents with FN compared to healthy controls.

Specific aim #3: Demonstrate that four weeks of auricular neurostimulation improves nausea while strengthening the vagal tone and the abnormal resting state brain connectivity in female adolescents with FN compared to baseline and to more resemble that of healthy controls.

Hypothesis: 3a) Compared to baseline (pre-stimulation), there will be reduction in nausea and concurrent symptoms in the active compared to sham neurostimulation group after 4 weeks of therapy. 3b) Active neurostimulation therapy will increase vagal tone compared to baseline and also increase the rsFC between the vmPFC and amygdala in female adolescents with FN.

C. BACKGROUND, SIGNIFICANCE, AND RATIONALE

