One of the primary concerns in interpreting fMRI data obtained in children and in making comparisons across age groups involves the significant developmental changes in brain morphology that occur during childhood and adolescence. Although the majority of brain growth occurs prior to the age of 5 years, it has been estimated that approximately 5-8% of cerebral growth occurs between the age of 5 years and adolescence.⁴¹⁻⁴⁴ Furthermore, brain maturation proceeds at different rates in different regions of the brain. Concerns have been raised regarding the possible effects of these developmental changes on the process of spatial normalization, which involves transformation of images to a common stereotactic space based on an adult-derived template. The latter process is necessary in order to make direct voxel wise comparisons across subjects and subject groups. Recent studies do support the feasibility of making such comparisons within a common stereotactic space, suggesting that anatomical differences between the atlas transformed brain morphology of children (aged 7 to 8 years) and adults are minimal, relative to the level of resolution possible with current functional imaging and that would not result in spurious functional differences.^{45, 46} This study will include only adolescents who are at least 12 years of age, further minimizing any potential developmental effects.

Study Population

80-100 adolescents with chronic nausea and a subgroup of 15 patients with IBS as well as 15 healthy controls, between ages of 12-18 years, will be enrolled. All subjects will undergo gastric motor function and HRV testing at baseline followed by four weeks of auricular neurostimulation or sham therapy. By definition, all adolescents in this study will have no clear explanation for their symptoms after undergoing medical workup per standard of care.

Inclusion Criteria (Nausea and IBS Groups):

- Children aged 12 years to 18 years who provide written assent and whose parents provide written permission for participation

- English-speaking and able to verbalize their condition and concerns about nausea, pain and other symptoms
- Subjects will meet Rome IV criteria for functional nausea as determined by a pediatric gastroenterologist
- Subjects included in the IBS group will meet Rome IV criteria for Irritable Bowel Syndrome

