- Patients must have an intact external ear that is free of infection or severe dermatological conditions, have stable vital signs for their respective age, no history of seizures and no currently implanted electrical device
- Subjects included in the FN group include those who meet Rome IV criteria for functional nausea and have:
 - 1) autonomic imbalance with low vagal tone defined as baseline resting supine RMSSD value 2 or more standard deviations below the mean on HRV measurements, and
 - 2) normal gastric motor function (absence of gastroparesis or impaired accommodation). The gastric motor function and HRV tests will be compared to normative values obtained through a separate, ongoing, IRB-approved protocol (# 1030543-2)

Exclusion Criteria (Nausea and IBS Groups):

- Other pain-related diseases or somatization disorder
- Mental retardation or pervasive developmental disorder or epilepsy
- Psychosis
- Genetic or chromosomal disorders
- Pregnancy
- Subjects who admit to substance abuse during screening
- Patients with findings of peptic ulcer disease, H.pylori gastritis, celiac disease, inflammatory bowel disease, allergic disorders, or any chronic condition or medication that may cause nausea or pain
- Patients who are treated with opioids or who had any changes in their medical regimen in the past four weeks prior to study
- Patients with a history of allergy to adhesives
- Patients with a lactose intolerance

Study Design Overview

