meal as previously performed in children and adults.^{19,77,78} End-tidal breath samples are collected before and at regular intervals after ingestion (15, 30, 45, 60, 90, 120, 150, 180, 210 and 240 min). Breath samples are analyzed for ¹³CO₂ content using isotope ratio mass spectrometry (Cairn Diagnostics, Brentwood, TN, USA) as previously described.⁷⁷ The time at which half of the ¹³CO₂ is excreted in the breath is defined as the gastric emptying half time (t_{1/2}). Subjects are classified as delayed (t_{1/2}>90th percentile) vs normal (10th<t_{1/2}≤90th percentile) gastric emptying based on control data obtained through separate study.

Regulatory status

The ¹³C-Spirulina Gastric Emptying Breath Test (GEBT) is FDA approved (PMA #P110015) for use in adults (see attached forms and intended use statement below).

Intended Use Statement

The Gastric Emptying Breath Test (GEBT), to be used with the GEBT test meal, is intended for use in the measurement of the rate of gastric emptying of solids and as an aid in the diagnosis of delayed gastric emptying (gastroparesis) in adult humans who are symptomatic for gastroparesis. For these purposes, the test system utilizes a Gas Isotope Ratio Mass Spectrometer (GIRMS) for the measurement of the ratio of ¹³CO₂ to ¹²CO₂ in breath samples.

The GEBT procedure will be administered under supervision of a health care professional although no specialized facilities or specially licensed personnel are required.

Description of the Gastric Emptying Breath Test (GEBT)

The GEBT is a non-radioactive breath test that uses the stable isotope, carbon 13 (¹³C).⁸⁰ ¹³C stable isotope labeling is inherently safe as 1.1% of all the carbon in nature, our bodies and in the food we eat is ¹³C, with the remaining 98.9% being ¹²C. The test consists of a breath collection kit with subsequent analysis of the breath samples by Gas Isotope Ratio Mass Spectroscopy (“GIRMS”). The breath collection kit includes a standardized test meal that contains freeze-dried ¹³C labeled Spirulina.

After an overnight fast, the patient consumes the test meal consisting of:

- a dried scrambled egg mix containing approximately 100 mg of ¹³C-Spirulina. The 13C-labeled Spirulina/scrambled egg mix is rehydrated with potable water just before cooking in a microwave oven
- Six (6) Nabisco PREMIUM Saltine crackers
- Six (6) ounces of potable water

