The SDT is a simple and non-invasive measure of sensation to gastric distention. It has good reproducibility and correlates fairly well with barostat studies of gastric accommodation.^{81,82 20} The maximum tolerated gastric volume and satiety is recorded after subjects ingest a nutrient formula at a predetermined rate until reaching maximal satiety (see protocol below). The volume ingested when reaching a satiety score of 5 corresponds to the maximal ingested volume (i.e. drinking capacity). The SDT measurements will be compared to normative data from a separate study. A drinking capacity (kcal) of <5th percentile for age and gender will classify a patient as impaired gastric accommodation.

Studies will be carried out on a separated day from the above GEBT, also in the morning after an overnight fast. Height and weight of subjects will be recorded prior to testing. Subjects will ingest a room temperature liquid nutrient drink (Ensure Original Vanilla; Abbott Laboratories, IL, U.S.) containing 220kcal per 237ml, 18% protein, 11% carbohydrates and 9% lipids. One of two beakers will be filled with the drink by a research coordinator or nurse at a rate of 30 ml/min. The subject will be instructed to ingest the drink at the filling rate by alternating the beakers. Every 5 min, they will be asked to score their satiety and symptoms of nausea, bloating, pain, burning sensation and vomiting on a scale 1-5: 1= no sensation; 2=first sensation; 3=mild sensation; 4=moderate sensation and 5= maximum sensation. The maximum tolerated gastric volume (kcal), i.e. drinking capacity, is recorded after subjects reach maximal satiety with a score of 5 at which point they will cease drinking. At the same 5 min intervals, subjects will also be asked to circle their nausea on a validated pictorial nausea severity scale (BARF scale) 0-10.⁸³ Twenty minutes after completing the test, the subjects will again score the above symptoms on scale 1-5. A research coordinator or nurse will assist the children with completing the scores and carefully explain symptoms such as satiety as their fullness and opposite of desire to eat.

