fMRI-guided connectivity analysis: We have developed a novel *fMRI-guided connectivity analysis* in previous investigations by [name] to determine the distribution of an arousal network by using a seed region in a specific brain area of interest. In this protocol, we will examine resting state functional connectivity with amygdala as the seed region of interest and its coupling with prefrontal cortex areas as well as insula and hypothalamus as key nodes of the emotional arousal neurocircuit and internal awareness.

Statistical Analysis

Data Management

The data gathered will be entered into REDCap data system with each ID having a unique identifier for each participant. REDCap is a secure, web-based application for building and managing online databases. All data will be de-identified and samples will only have a unique identifier that will link the unique identifier with the patient's name.

The REDCap clinical database will be maintained by the Department of Quantitative Health Sciences, at the Children's Research Institute under the direction of [name].

Missing Data Handling

Missing Data: Every effort will be made to avoid missing data. Using logistic regression, the pattern of missing data will be explored. Assuming the data are missing at random (MAR) multiple imputations for items will be used. Data analysis overview: Summary statistics, such as mean, median, standard deviation, range and correlation will be used as a first step to examine data. To satisfy parametric assumptions, we may perform transformations with justifications if possible and otherwise use non-parametric tests. We will use CART and biological and physiological information to identify interactions when formulating regression models. Statistical software employed for data analysis will be: Cytel StatXact, SAS version 9.4, Salford System CART for trees, SPSS Version 24. The power calculation was made using PASS 13.'

Power

Aim 1. We will summarize characteristics by the groupings.

Aim 2. See fMRI analysis section below

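### Aim 1's two gastric motor subgroups are cut at healthy-control percentiles and only summarised, so their existence cannot be refuted; the three groups also overlap and leave some patients out

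*Combined protocol and SAP*

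**What the plan says.** All references are to the combined protocol and SAP.

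- **Specific Aims, aim 1.** The hypothesis is that "Adolescents with chronic nausea form subgroups based on clinical, physiologic and psychological parameters", and it lists three: FN, gastroparesis and poor gastric compliance.
- **Study Population.** Enrolment is "80-100 adolescents with chronic nausea and a subgroup of 15 patients with IBS as well as 15 healthy controls".
- **Gastric Emptying Breath Test.** The rule is "Subjects are classified as delayed (t_{1/2}>90th percentile) vs normal (10th<t_{1/2}≤90th percentile", with "gastric emptying based on control data obtained through separate study". The size of that control sample is not given.
- **Satiety Drink Test.** The rule is "A drinking capacity (kcal) of <5th percentile for age and gender will classify a patient as impaired gastric accommodation".
- **Inclusion Criteria, FN group.** FN needs two things besides Rome IV functional nausea: "autonomic imbalance with low vagal tone defined as baseline resting supine RMSSD value 2 or more standard deviations below the mean on HRV measurements", and "normal gastric motor function (absence of gastroparesis or impaired accommodation".
- **Statistical Analysis, Power, Aim 1.** The whole entry reads "We will summarize characteristics by the groupings". No test, interval, reference rate or expected group size accompanies it.

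**The concern.** A cut at a healthy percentile fixes in advance the share of healthy people who fall beyond it. If the groups are then only described, both motor groups will be populated whether or not nausea patients have abnormal stomachs. The trial could report gastroparesis and poor-accommodation phenotypes that are no more than the tail of normal, and would take those patients out of FN.

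The rules also do not sort patients cleanly into the three groups:

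- A patient with both delayed emptying and low drinking capacity belongs to two groups, and no rule says which takes precedence.
- A patient with normal gastric tests whose RMSSD is less than 2 SD below the mean belongs to none.
- A patient with t1/2 at or below the 10th percentile is neither delayed nor normal under the breath-test rule, yet can satisfy the FN inclusion wording on motor function.

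This matters because Aim 1 is meant to define FN as an entity, and because subjects classified as FN form the 15-patient nausea group in the fMRI sub-study.

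**Working it through.** The plan states no expected group size or power for Aim 1, so there is no figure to reproduce. The checks below start from its cuts and its enrolment range.

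**1. Expected group sizes if nausea patients have normal stomachs.** The share beyond each cut is 10% (above the 90th percentile) or 5% (below the 5th).

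| | N = 80 | N = 100 |
|---|---|---|
| Delayed, N × 0.10 | 8 (95% binomial range 3-14) | 10 (5-16) |
| Impaired, N × 0.05 | 4 (1-8) | 5 (1-10) |
| P(at least one delayed), 1 − 0.90^N | >0.999 | >0.999 |
| P(at least one impaired), 1 − 0.95^N | 0.983 | 0.994 |

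**2. Patients with either motor label.** If the two tests are independent, the share is 1 − 0.90 × 0.95 = 0.145, which is 11.6 of 80 or 14.5 of 100. With complete overlap it is 10%; with no overlap it is 15%.

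**3. Patients with both labels.** If independent, 0.10 × 0.05 = 0.005, or 0.4 of 80 and 0.5 of 100. With complete overlap it is 5%, or 4 to 5 patients. A real motor disorder would raise these counts.

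**4. Patients in none of the three groups.** The documents do not give the distribution of RMSSD in nausea patients, so this needs assumptions: normal scale with the same SD as controls, normal motility, RMSSD independent of the gastric tests, and rapid emptiers counted as having normal motor function. For a downward mean shift of s SD, the share with low RMSSD is Φ(−2 + s), and the share in no group is 0.90 × 0.95 × [1 − Φ(−2 + s)] = 0.855 × [1 − Φ(−2 + s)].

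| Shift s | Low RMSSD | In no group |
|---|---|---|
| 0 | 2.3% | 84% |
| 1 SD | 15.9% | 72% |
| 2 SD | 50% | 43% |
| 2.5 SD | 69.1% | 26% |

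**5. What a comparison with the built-in rate could show.** The smallest counts whose exact (Clopper-Pearson) 95% lower limit exceeds the built-in rate are 15/80 or 17/100 for delayed (against 10%), and 9/80 or 11/100 for impaired (against 5%). With a true delayed share of 15%, that count is reached with probability 21% at N = 80 and 33% at N = 100; with a true share of 20%, 65% and 81%. These figures treat the control percentiles as known.

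**The case against.** **The plan holds more than the one Aim 1 sentence.** The drink-test section compares results with normative data, and the FN criteria compare gastric and HRV tests with norms. The NDT analysis section has a t-test or Mann-Whitney test at 5%, and the section on continuous and ordinal variables plans distribution summaries and tree analysis. This stands as far as it goes: part of the display against norms is already foreseen. But the NDT test names no groups, the breath test has nothing equivalent, and none of these analyses sets the share beyond a cut against 10% or 5%.

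**Percentiles are not the only evidence.** Aim 1 also uses questionnaires, PAGI-SYM covers gastroparesis symptoms, and T_max will help interpret the breath test. These could add clinical support to a label, but the stated classification rules use the percentile alone.

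**Four stronger readings are tempting but not supported:**

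- *That the whole Aim 1 hypothesis cannot fail.* It also says FN shows high anxiety and emotional arousal. Neither is part of the FN entry rule, so a summary by grouping could contradict it. Only the existence of the two motor groups escapes refutation.
- *That rapid emptiers are a large unclassifiable group.* The FN criterion explains normal motor function as the absence of two named abnormalities, and a rapid emptier with adequate drinking capacity meets that. What remains is a missing label in the breath-test rule and wording to reconcile.
- *That the defect reaches the randomised comparison or all of hypothesis 3b.* Randomisation takes the chronic-nausea cohort, and the Power section analyses vagal tone in nausea subjects. Motor-labelled patients are not lost from either.
- *That most patients will fit no group.* This depends entirely on the unknown RMSSD shift.

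**Conclusion.** The concern holds for the two motor subgroups and for the grouping scheme. With normal stomachs, 8-10 of 80-100 patients would be labelled delayed and 4-5 impaired, and 10-15% would carry at least one label (14.5% under independence). The plan has no analysis that separates this from a real excess. A real excess may well exist; the plan as written could not show it.

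The groups are neither mutually exclusive nor exhaustive. The share in no group runs from about 84% to 26% as the assumed RMSSD shift goes from none to 2.5 SD, and no single value in that range can be taken from the documents.

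The expected counts rest on the control percentiles being accurate for this population. The consequence is limited to Aim 1 and to FN classification for the fMRI sub-study.

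**What to change.** In the Aim 1 entry of the Statistical Analysis section:

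1. Report the proportion beyond each motor cut with an exact 95% CI, beside the rate built into the cut (10% delayed, 5% impaired).
2. Show the full distributions of t1/2 and of drinking capacity in kcal against the normative data.
3. State that the control percentiles are themselves estimates from a separate study, and give its size. Their error makes any comparison weaker than the exact interval suggests.
4. Interpret the estimate and its interval directly. A rule that a subgroup counts as present only if the lower limit exceeds the built-in rate is not advised: at a true delayed share of 15% it would miss the excess 67-79% of the time (1 − 0.33 and 1 − 0.21).
5. Replace the three-group list with a full cross-classification: delayed yes/no, impaired accommodation yes/no, low vagal tone yes/no. That gives 2 × 2 × 2 = 8 cells, including the overlap cells and the cell with no abnormality.
6. Reconcile the breath-test definition of normal emptying with the FN criterion for normal motor function, so that a t1/2 at or below the 10th percentile has one stated status for FN.

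The cost is SAP wording and one extra table, with no new data. The downside is that Aim 1 may have to report that a motor subgroup is not clearly larger than expected in healthy adolescents.

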Subjects will enter a 4-week, prospective randomized, double blind sham controlled treatment trial with the FDA-approved and commercially available EAD manufactured by Key Electronics (Jeffersonville, IN, USA) and distributed by Innovative Health Solutions (Versailles, IN, USA). The device is cleared under the BWK classification, with intended use in the practice of acupuncture by qualified practitioners of acupuncture as determined by the states. EAD is an ambulatory, neurological device which consists of a battery powered, externally affixed generator with 4 wire leads attached to 3 electrode/ needle arrays and one single point needle. The arrays are designed to produce a field effect similar to surgically implanted peripheral neurostimulators. The electrodes will be placed percutaneously in the external ear with the help of a transilluminator to visualize the neurovascular bundles. Three electrodes will be placed on the ventral and one on the dorsal aspect of the ear. The electrodes will be taped and secured behind the ear next to the generator itself which is secured to the skin with adhesive. The entire device may be covered by longer hair. The placement of the devices is within standard of care by properly trained medical doctors as already completed trial at CHW (IRB# 689519-17). Training of MDs has been performed by [name] or [name] as representatives of Innovative Health Solutions. Training of other involved physicians may be performed if protocol approved. 40-50 subjects will receive the active EAD device while 40-50 subjects will receive an inactive device that is identical to the active device but lacking the battery.

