Patients will be told that they may or may not feel a slight flushing or tingling sensation after device placement. The electrode/needle arrays are implanted according to the individual's arterial and cranial nerve anatomy. The exact location of the implantation may vary slightly from person to person but is determined by both knowledge of auricular neuro-anatomy and visualization of the neurovascular bundles by trans-illumination (IHS, Versailles, IN, USA). The points will be targeted by four-point electrical stimulation using the EAD device after carefully disinfecting the ear. The small device will be positioned and secured behind the ear similar to a hearing aid, which may be covered by hair. Neurostimulation will be delivered below sensation threshold continuously for 5 consecutive days. The EAD device will be applied by a trained MD. Subjects will remove the device independently at home and discard them as they are non-functioning after 5 days (5 days battery life). If a device is lost or broken, the research team will attempt to schedule placement of a new EAD within 1 day if you wish. The devices are easily removed by removing the tapes and adhesives. Before and during the treatment trial, subjects and parents will complete questionnaires as shown in Table 1.

The EAD Surgical kit consists of :

- an alcohol swab
- prep and stay swab
- round fixation plasters
- fixation plasters to fasten the generator
- Steri-strip adhesive vial
- Sterile wire harness pack
- Generator
- Tweezers
- Surgical marker
- Transilluminator

EAD placement details:

1. A research coordinator in the GI office will be asked to open the package and obtain either a true device or a control device as outlined in a randomization scheme provided by the statistician. This research coordinator will document the patient ID, name and the device serial number in the study database and whether assigned to an active vs inactive device. This lead research coordinator will be the only unblinded person and she will not be involved in any patient contact or other parts of the study.

2. The neurostimulator placement will be performed as directed and per EAD training protocol instructions identically to prior CHW IRB approved trial.

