3. Before neurostimulator placement, the subject should be advised that some discomfort is normal at first but should report if the discomfort persists or gets worse after a few minutes. The patients should be advised that they may feel a slight pulsing sensation and perhaps a warming sensation in the ear to which the electrodes are affixed. The pulsing and warming sensation may disappear after approximately 5 minutes. If the discomfort level increases the offending electrode can be slightly repositioned until the patient's discomfort level decreases to an acceptable level.
4. Device placement will take approximately 5 minutes. The patient will remain at rest for the next 5 minutes.
5. The subject will be advised not to immerse the device in water as the device is water resistant but not water proof. If showering or washing their hair, subjects will be instructed to place a dry wash cloth or plastic such as Press n' seal over the area to help protect the device. Subjects will be given a contact person (primary investigator and research coordinator) to call if they are having any problems with the device or if it falls off.
6. The patient will be instructed on removing the device after 5 days. If not comfortable doing so or unable to carry out the instructions, the patient may be seen that day for removal by one of the investigators.
7. At the end of the study (post-neurostimulation #1), subjects will be asked to guess their group allocation to test blinding.
8. The patient will be asked to return the used device for proper disposal when they return for their follow-up appointment.
9. The subject will be given a handout with information (attached) on device handling, exact date and time of device removal and date and time to return.
10. The subject will be advised to refrain from using any new or as needed anti-emetic or pain medications.
11. The subject is dismissed.

Optional fMRI sub-study

Participants will be given the option to participate in the fMRI sub-study. Post menarche patients must yield a negative urine pregnancy test on the day of each scan. Participants will then be escorted to the fMRI scanner in the lower level of FH where they will complete the safety screening questionnaire. The patient will be given the option of lying down in the mock scanner prior to their first fMRI scan.

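### The protocol contradicts itself on whether active stimulation can be felt, so the adequacy of a batteryless sham cannot be judged, and the one planned blinding check is late and has no stated analysis

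*Combined protocol and SAP*

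**What the plan says.** All of the following is in the combined protocol and SAP, section F unless noted.

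- **Intensity** (EAD treatment protocol): "Neurostimulation will be delivered below sensation threshold continuously for 5 consecutive days".
- **Script A** (same section): "Patients will be told that they may or may not feel a slight flushing or tingling sensation after device placement".
- **Script B** (EAD placement details, step 3): subjects are to be advised that "they may feel a slight pulsing sensation and perhaps a warming sensation in the ear to which the electrodes are affixed". Step 3 adds: "The pulsing and warming sensation may disappear after approximately 5 minutes".
- **Sham** (EAD treatment protocol): "an inactive device that is identical to the active device but lacking the battery". Of the device generally: "The electrodes will be placed percutaneously in the external ear". The sham therefore has needles but no current.
- **Blinding**: the trial is described as double blind, and only one coordinator, who has no patient contact, holds the key. Step 7 of the placement details has subjects guess their allocation at post-neurostimulation #1. No analysis of that guess is described.
- **Weekly record** (Measurements and Data Collection): at each placement, staff ask about side effects over the previous week. Nothing specifically asks whether the device was felt.
- **Primary outcome** (Statistical Analysis, Aim 3): the weekly Nausea Severity Scale total after 4 weeks. It is a revised form of the Abdominal Pain Index and is completed by the patient.

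**The concern.** A pulse that is felt and then fades is not sub-threshold, so the intensity statement and step 3 disagree on the fact that decides whether this sham can work. A needle-only sham can match the look of the active device and the feel of insertion. It cannot match an electrical pulse.

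If the pulse is perceptible, subjects are told what to look for before each of the four weekly placements (visits 3 to 6), and they then rest for 5 minutes, which overlaps the period in which the sensation is said to last. The primary outcome and most secondary outcomes are self-reports, so a belief about allocation that differs by arm would feed directly into the treatment contrast, most plausibly in favour of the device.

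As planned, the trial would have little evidence at the end to show whether this happened.

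**Working it through.** **1. The passages side by side.**

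| Question | EAD treatment protocol | Placement details, step 3 |
|---|---|---|
| Can the current be felt? | No (sub-threshold) | Possibly, for about 5 minutes |
| Sensations named to subjects | Flushing, tingling | Pulsing, perhaps warming |
| Wording | Explicitly two-sided | Possible, not certain |

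**2. What follows from each reading.**

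- *Not felt:* there is no electrical cue. Step 3 may raise a false expectation, but equally in both arms, so the active-versus-sham contrast is not biased by it.
- *Felt:* active subjects can have a cue that the sham cannot produce electrically, and step 3 has named it.

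The documents do not settle which reading applies.

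**3. The plan's own figure.** About 40 per arm less 12% dropout: 40 × 0.88 = 35.2, which reproduces the stated figure of about 35. The detectable difference is left as a placeholder in the power text. For scale, a two-sample t-test with 35 per arm, two-sided 5% and 80% power detects 0.68 SD.

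**4. Size of the possible bias (illustration).** Let g be the excess share of active over sham subjects who sense the device and conclude that it is active. Let b be the resulting shift in self-report, in SD. Neither is given in the documents, so both are assumed. Bias = g × b. With no true effect, the false-positive rate is the rejection probability of a two-sided 5% t-test with noncentrality g·b·√(35/2) on 68 degrees of freedom.

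| g | b = 0.2 | b = 0.3 | b = 0.5 |
|---|---|---|---|
| 0 | 0 SD; 5% | 0 SD; 5% | 0 SD; 5% |
| 0.25 | 0.05 SD; 5.5% | 0.075 SD; 6.1% | 0.125 SD; 8.1% |
| 0.50 | 0.10 SD; 7.0% | 0.15 SD; 9.5% | 0.25 SD; 17.8% |
| 0.75 | 0.15 SD; 9.5% | 0.225 SD; 15.3% | 0.375 SD; 34.0% |

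The row g = 0 is the case that the intensity statement describes. The largest entry is 0.375 / 0.68 = 55% of the detectable difference. Sham sensation reduces g: if 50% of active and 20% of sham subjects report the cue, g = 0.30, and at b = 0.5 the bias is 0.15 SD (9.5%) rather than 0.25 SD (17.8%).

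**5. What the allocation guess could show.** With 70 guesses, 44 correct (63%) are needed to exceed chance at one-sided 2.5%. The probability of reaching that is 36% if true correct guessing is 60%, 70% if it is 65%, and 92% if it is 70%. Suppose every subject who feels the cue guesses active and everyone else guesses sham, with no sham subject feeling it. Correct guessing is then (1 + g)/2, or 62.5% at g = 0.25, so the check could well miss unblinding of that size. A guess made only after 4 weeks is also confounded with symptom response: subjects who improved may guess active for that reason.

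**The case against.** The case on the other side is substantial, and much of it stands.

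- **A reader might infer that the script by itself unblinds the trial.** It does not. The advice is not arm-specific, and those who give it are blinded. It matters only if active subjects feel the current.
- **A reader might infer that subjects are told to expect pulsing.** They are told that it may occur. The two scripts are logically close, and script A names tingling, itself a current-like sensation.
- **A reader might infer that the sham produces no sensation.** The documents do not describe what sham subjects feel. Absence of an electrical pulse is secure. Absence of warming is not, because both arms have percutaneous electrodes. In the investigators' completed trial, ear discomfort was reported by three active and three placebo subjects. That shows no imbalance, but six reports do not measure pulsing.
- **A reader might infer that the placing physician is cued as well.** Repositioning in step 3 is prompted by discomfort, which can arise in either arm, not by reports of pulsing.
- **A milder reading reconciles the texts:** step 3 could describe the first minutes after placement and the sub-threshold statement the 5-day delivery. This is possible, but the protocol does not say so, and a brief cue at each placement would still be a cue.
- **Blinding is not unmonitored.** The allocation guess and the weekly side-effect questions exist. The guess is late and has no stated analysis, and the side-effect questions do not specifically record sensation.

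What remains is the contradiction itself, and a check too weak to resolve its consequences.

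**Conclusion.** The concern holds in conditional form. The protocol contradicts itself on whether active stimulation can be felt and gives subjects two different scripts. If the current can be felt, the sham cannot match the electrical pulse, subjects have been told of that cue, and the self-reported primary outcome is open to bias in favour of the device. If it cannot be felt, this route to bias is closed.

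On the assumed ranges (g from 0 to 0.75, b from 0.2 to 0.5 SD, 35 per arm, unadjusted two-sided 5% t-test), bias runs from 0 to 0.375 SD and the false-positive rate from 5% to 34%. These figures show scale and are not predictions. The documents do not support the stronger conclusion that the trial is, or will be, unblinded. They do leave a reader unable to judge whether the sham is adequate, and as planned the trial would collect little to settle it afterwards.

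**What to change.** 1. Reconcile the EAD treatment protocol with step 3 of the placement details on whether stimulation can be felt. No view is taken here on intensity.
2. Replace the two scripts with one neutral script consistent with that answer, read verbatim in both arms at every placement. The step 3 wording should not be deleted before the reconciliation, since that would prejudge the answer and, if the current is felt, would leave the cue in place without notice of it.
3. Soon after the first placement, collect an allocation guess with its reason, or a brief sensation item. Keep the guess at post-neurostimulation #1.
4. Tabulate both by arm and specify a blinding-index analysis in the SAP.
5. Label any analysis by sensation or guess as supportive only, because both are post-randomisation variables.

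The cost is protocol, script and handout wording, one short item, and a paragraph in the SAP. The item may draw some attention to sensation, so it should be neutrally worded and identical in both arms. Early sensation data cannot be reliably reconstructed later.
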